6 INTENDED USE / INDICATION FOR USE

The BreathID[®] System ¹³C-Methacetin Breath Test (MBT) is to be used for the identification of clinically significant portal hypertension (CSPH), as defined by an Hepatic Venous Pressure Gradient (HVPG) ≥ 10 mmHg in patients with liver cirrhosis independent of disease etiology, without a history of clinical decompensation (variceal bleeding, uncontrolled ascites, hepatic encephalopathy and/or hepatorenal syndrome).

7 PROPOSED CLINICAL ALGORITHM USING THE MBT

The company's goal is to develop a point-of-care device for the identification of clinically significant portal hypertension (CSPH).

The company proposes to train a selected MBT-based variable that can reliably identify clinically significant portal hypertension (defined as HVPG ≥ 10 mmHg) in patients with compensated liver cirrhosis. This will enable the use of a dichotomous measure from MBT to assess CSPH by means of rule-in or rule-out or both.

Exalenz Bioscience Ltd.	Last update on: Nov 21, 2016
Study Title: Clinical Study of the BreathID[®] MCS System to train the algorithm for the ¹³C-Methacetin Breath Test (MBT) in assessment of Portal Hypertension in Patients with Compensated Liver Cirrhosis	Protocol No.: CSPH-EX-0414 Version: 1.5
Document N^o: CSD00076	Page 30 of 72

8 MBT SHORT DESCRIPTION

8.1 MBT Overview

The MBT is a non-invasive test for assessing liver metabolic capacity to metabolize ¹³C-Methacetin in order to assess presence of CSPH. The *BreathID[®] MCS System* consisting of the *BreathID[®] MCS* device and a test kit containing a breath collection cannula and a non-radioactive isotope ¹³C-Methacetin solution, which measures and computes the ratio between ¹³CO₂ and ¹²CO₂ in the patient's exhaled breath.

For more details please refer to the study Investigator Brochure.

The device is based on an FDA cleared device (510k#: K130524) for assessment of *H. pylori* infection in the stomach utilizing ¹³C-Urea as a substrate for the bacterial urease. Performance and safety of the device utilizing the ¹³C-Methacetin substrate for assessment of liver function, have been studied in thousands of patients worldwide, including in a large US pivotal study – under IDE G080107 – of over 400 patients with chronic liver disease from 11 participating sites (including 141 patients with biopsy proven cirrhosis),⁽⁶⁹⁾ which validated the safety of the MBT.

8.2 ¹³C-labelled Substrate: ¹³C-Methacetin

The ¹³C-labeled Methacetin has been selected as the test substrate. ¹³C-Methacetin is a white, crystalline powder bearing the chemical name [N-(4-Methoxy phenyl) acetamide]. ¹³C-Methacetin is rapidly absorbed and metabolized exclusively by hepatic microsomal function oxidase via O-demethylation, mainly by cytochrome P450 1A2, into acetaminophen (also known as paracetamol, Tylenol[™], and n-acetyl-p-aminophenol or APAP) and formaldehyde.⁽⁵¹⁻⁵⁶⁾ Formaldehyde is then transformed, through two successive oxidative steps, into ¹³CO₂. The rate limiting factor in this process is the O-demethylation performed by the liver cytochrome CYP450.⁽⁵⁷⁾ The general reaction is described in the following scheme:

Exalenz Bioscience Ltd.	Last update on: Nov 21, 2016
Study Title: Clinical Study of the BreathID[®] MCS System to train the algorithm for the ¹³C-Methacetin Breath Test (MBT) in assessment of Portal Hypertension in Patients with Compensated Liver Cirrhosis	Protocol No.: CSPH-EX-0414 Version: 1.5
Document N^o: CSD00076	Page 31 of 72

[figure not shown]

Figure 7: Oxidative Cleavage of Methacetin to Acetaminophen and Formaldehyde

The resultant ¹³CO₂ can be measured in the exhaled breath. The amount of metabolized Methacetin indicates the capability of the liver to accomplish one of its main physiological tasks and has been shown to correlate with liver fibrosis and cirrhosis.^(66, 70-72)

¹³C-Methacetin meets all of the qualifications for a liver function test substrate: It is a non-toxic small molecule, is administered orally, is rapidly absorbed and is exclusively metabolized by the liver. Furthermore, ¹³C can be easily synthesized into a key location within this molecule. No adverse events have been reported when using this substance, including in vulnerable populations, and the compound remains stable over time.

8.2.1 ¹³C-Methacetin Safety

The ¹³C-Methacetin substrate is a well-known diagnostic reagent that has been described in the literature and used for over 100 years in general and for over 30 years specifically for breath testing by leading researchers around the world (US, Europe and Japan). As previously mentioned, there have been no reports of any complications with the use of this substance. The

Exalenz Bioscience Ltd.	Last update on: Nov 21, 2016
Study Title: Clinical Study of the BreathID[®] MCS System to train the algorithm for the ¹³C-Methacetin Breath Test (MBT) in assessment of Portal Hypertension in Patients with Compensated Liver Cirrhosis	Protocol No.: CSPH-EX-0414 Version: 1.5
Document N^o: CSD00076	Page 32 of 72

main metabolite of Methacetin is acetaminophen which has wide routine clinical use at much higher doses than orally administered dose of ¹³C-Methacetin of 75mg used in this study.

In current literature regarding pre-clinical and clinical studies performed with Methacetin, results from a total of 2987 individuals (2021 chronic liver disease patients including critically ill patients and 966 controls) were reported in 73 publications, including neonates,⁽⁷³⁾ infants,⁽⁷⁴⁾ healthy adults, adults with various forms of liver disease (including toxic injury), pregnant women⁽⁷⁵⁾ and the elderly - with no reports of adverse events. MBT has also been used in patients with Acute Liver Failure. Some of these data were developed utilizing the Exalenz device and substrate, while the majority were performed with other similar systems.

Regarding internal unpublished data using our device and Methacetin, 1466 chronic liver patients (of these 278 cirrhotic - some before transplant) and 74 healthy controls/subjects without liver disease, have also been tested. No adverse events related to the substrate were experienced by the subjects

Toxicology testing results in animals and other information support the safe use of Methacetin in humans. Based on the acute toxicity studies in mice and rats where relatively high LD50 values of 1190mg/kg were administrated,⁽⁷⁶⁾ the Methacetin dose administered in human breath tests in adults of 75 mg, or approximately 1mg/kg, has a safety ratio in excess of 1000-fold.

Many studies using ¹³C-Methacetin for liver function assessment have been published. Representative references have been cited that support the conclusion that ¹³C-Methacetin is a “safe” molecule and that it has been used on high-risk population groups such as the elderly, neonates or pregnant women.^(60, 65, 77, 78) This provides further assurance that the ¹³C-Methacetin substrate is appropriate to use in breath tests intended for liver function assessment.

8.3 MBT Components

The following are the components of the *MBT System*: The *BreathID[®] MCS* device, the ¹³C-Methacetin substrate and the sampling kit containing breath collection cannulae.

The *BreathID[®] MCS* device will be provided by Exalenz Bioscience Ltd. The cannulae, accessories and the test substrate will be supplied in proper packaging and will bear all required labeling based on applicable regulatory requirements.

The solution administered orally to the patient is a 0.05% solution of ¹³C-Methacetin in purified water, supplied in amber thermoplastic polyester (PET) bottles with a child resistant plastic stopper (75mg of ¹³C-Methacetin in 150mL purified water). All bottles are for single use only and must be used solely for per-protocol investigational product administration. Each bottle

Exalenz Bioscience Ltd.	Last update on: Nov 21, 2016
Study Title: Clinical Study of the BreathID[®] MCS System to train the algorithm for the ¹³C-Methacetin Breath Test (MBT) in assessment of Portal Hypertension in Patients with Compensated Liver Cirrhosis	Protocol No.: CSPH-EX-0414 Version: 1.5
Document N^o: CSD00076	Page 33 of 72

contains a single test dose. The solution is manufactured at Taro Pharmaceutical Industries, Ltd., [name] and will be provided under the responsibilities of Exalenz Bioscience Ltd, [name].

All study test components must be stored in an environment according to the Investigator Brochure and product labeling guidance.

9 STUDY DESIGN

This study is a multicenter, non-randomized, blinded, cross-sectional comparative exploratory study comparing various MBT measures to HVPG.

This study will be used to train an algorithm using MBT measures and to select a cut-off to determine presence or absence of CSPH as defined by HVPG \geq 10mmHg.

10 STUDY OBJECTIVES

10.1 Efficacy Objective

The primary objective of the study is to develop an algorithm and its cut-off to detect CSPH, defined as HVPG \geq 10mmHg, based on the MBT.

10.2 Safety Objective

All adverse events, serious adverse events (SAE) and suspected unexpected serious adverse reactions (SUSAR) will be reported according to local regulations. The actual reporting is discussed in section 14. No breath-test related adverse events are expected. For more information please refer to the Investigator Brochure.

10.3 Secondary Objectives

1. To assess the ability of the MBT model to diagnose portal hypertension with HVPG \geq 12mmHg
2. To assess the ability of the MBT model to diagnose portal hypertension with HVPG \geq 20mmHg
3. To assess the correlation of MBT with HVPG readings

Exalenz Bioscience Ltd.	Last update on: Nov 21, 2016
Study Title: Clinical Study of the BreathID[®] MCS System to train the algorithm for the ¹³C-Methacetin Breath Test (MBT) in assessment of Portal Hypertension in Patients with Compensated Liver Cirrhosis	Protocol No.: CSPH-EX-0414 Version: 1.5
Document N°: CSD00076	Page 34 of 72

4. To Assess the effect of beta blockers or other confounding factors on the correlation of MBT with HVPG readings
5. Examine the effect of a single small (<3cm) HCC (hepatocellular carcinoma) on the correlation of MBT with HVPG tracings

10.4 Efficacy Endpoints

10.4.1 Primary efficacy endpoint

Binary diagnosis of CSPH, defined by HVPG ≥ 10 mmHg, correlated with an MBT result to be developed.

The relationship will be assessed on both sides of the definitive HVPG value to obtain a clinically significant MBT model/algorithm and its cut-off to be validated in a separate study.

10.4.2 Secondary efficacy endpoint

1. Binary diagnosis of portal hypertension with HVPG ≥ 12 mmHg
2. Binary diagnosis of portal hypertension with HVPG ≥ 20 mmHg
3. Correlation of MBT with HVPG readings
4. Assess the effect of beta blockers or other confounding factors on the correlation of MBT with HVPG readings
5. Examine the effect of a single small (<3cm) HCC (hepatocellular carcinoma) on the correlation of MBT with HVPG tracings

10.5 Safety Endpoints

Adverse Event reporting.

11 SUBJECT SELECTION

The study population will be essentially enrolled on a consecutive basis of able and willing subjects meeting all inclusion/exclusion criteria with clinically, imaging or biopsy proven liver cirrhosis without decompensation events in the past.

Most patients to be enrolled in the proposed study will be from centers in Europe with the addition of site(s) in the US. Based on expert opinion in the field of hepatology, the population to be enrolled from Spain and France is representative of patients with chronic liver disease in the

Exalenz Bioscience Ltd.	Last update on: Nov 21, 2016
Study Title: Clinical Study of the BreathID[®] MCS System to train the algorithm for the ¹³C-Methacetin Breath Test (MBT) in assessment of Portal Hypertension in Patients with Compensated Liver Cirrhosis	Protocol No.: CSPH-EX-0414 Version: 1.5
Document N^o: CSD00076	Page 35 of 72

United States. It is presumed patients in both countries have similar etiologies and prognosis and are being used interchangeably in multicenter clinical trials using HVPG testing.^(7, 8, 18)

11.1 Inclusion Criteria

1. Adult men or women (≥ 18 years of age)
2. Patient (or legal guardian) can sign an Informed Consent Form.
3. Known chronic liver disease with cirrhosis confirmed by either:
 - a. liver biopsy or
 - b. clinical (palpable left lobe, splenomegaly) and laboratory (platelets $< 150,000/\text{mm}^3$ or albumin $< 3.8\text{g/dL}$, or INR > 1.3) evidence of cirrhosis and/or
 - c. imaging studies by abdominal sonography, computer assisted axial tomography, or magnetic resonance imaging, showing a nodular liver and/or enlarged spleen and/or portosystemic collaterals with portal vein patency and/or minimal ascites, and/or colloid shift on a colloid-isotope liver-spleen scan or measurements of liver stiffness suggestive of cirrhosis
4. Europe: Indicated to undergo HVPG testing
US: Consented for HVPG
5. Can tolerate an overnight (8-hour) fast
6. For patients treated with statins: They have to be on a stable dose for at least 4 weeks prior to any study related tasks (MBT or HVPG measurement)
7. For patients treated with beta blockers: They have to be on a stable dose for at least 6 weeks prior to any study related tasks (MBT or HVPG measurement)
8. For patients who stopped their treatment with beta blockers: Their last dose should be at least 6 weeks prior to any study related tasks (MBT or HVPG measurement)

Note: In case patient has HCC, breath test has to be performed on the day of HVPG measurement.

11.2 Exclusion Criteria:

1. Decompensated cirrhosis as clinically defined by the occurrence of any of the following: ascites, hepatic encephalopathy, variceal bleeding (active upper GI bleeding) or hepatorenal syndrome
2. Renal failure (creatinine $> 2.5\text{ mg/dl}$)
3. Known acute renal tubular disease
4. Known hypotension (Systolic Pressure $< 100\text{mmHg}$)
5. Hypocoagulability defined as PT > 6 and INR > 2.3
6. Congestive heart failure (assessed clinically as NIHA > 2)

Exalenz Bioscience Ltd.	Last update on: Nov 21, 2016
Study Title: Clinical Study of the BreathID[®] MCS System to train the algorithm for the ¹³C-Methacetin Breath Test (MBT) in assessment of Portal Hypertension in Patients with Compensated Liver Cirrhosis	Protocol No.: CSPH-EX-0414 Version: 1.5
Document N^o: CSD00076	Page 36 of 72

7. Known pulmonary hypertension (right ventricular systolic pressure > 45 mm Hg,)
8. Uncontrolled diabetes mellitus (HBA1C >9.5gr%)
9. Concurrent prednisone or immunosuppressive treatment, if therapy and/or response to treatment are not stable for at least 3 months
10. Documented hepatocellular carcinoma lesion larger than 3cm and/or multifocal lesions and/or evidence of vascular invasions
11. Gastric bypass surgery or extensive small bowel resection
12. Total parenteral nutrition
13. Any organ transplant recipient
14. Pregnant or breast feeding
15. Allergy to acetaminophen and/or other related medications.
16. Documented drug-related concurrent hepatotoxicity or drug-related silent steatosis or drug-related fibrosis (e.g. amiodarone, methotrexate and tamoxifen).
17. Uncontrolled malabsorption or diarrhea
18. Documented non-cirrhotic PHT, partial / complete portal venous occlusion, hepatic venous occlusion, previous PHT surgery, or placement of a transjugular intrahepatic portosystemic shunt (TIPS)
19. Primary or secondary biliary cirrhosis, primary or secondary sclerosing cholangitis, hepatic sarcoidosis, or other cholestatic disorders
20. Subjects unable to perform the MBT within 7 days of HVPG procedure
21. Subject should not have taken any of the following for at least 48 hours prior to the breath test: Acyclovir , allopurinol, carbamazepine, cimetidine, ciprofloxacin, daidzein, (herbal) disulfiram, echinacea, enoxacin, famotidine, fluvoxamine, methoxsalen, mexiletine, montelukast, norfloxacin, phenylpropanolamine, phenytoin, propafenone, rifampin, terbinafine, ticlopidine, thiabendazole, verapamil, zileuton or any medication that might interfere with Methacetin metabolism or might affect CYP 1A2
22. Subject should not have taken amiodarone within the last 30 days prior to the breath test or HVPG procedure
23. Splenomegaly secondary to inflammation/infection or hematologic malignancy.
24. Last dose of HCV treatment received within the last 3 years.

11.3 On the day of the MBT:

1. 8 hours fasting prior to MBT including all PO morning medications except for beta blockers
2. No Smoking on the day of the MBT

Exalenz Bioscience Ltd.	Last update on: Nov 21, 2016
Study Title: Clinical Study of the BreathID[®] MCS System to train the algorithm for the ¹³C-Methacetin Breath Test (MBT) in assessment of Portal Hypertension in Patients with Compensated Liver Cirrhosis	Protocol No.: CSPH-EX-0414 Version: 1.5
Document N^o: CSD00076	Page 37 of 72

3. No caffeine within 24 hours prior to MBT
4. No paracetamol (acetaminophen) based medications within 24 hours prior to MBT
5. No general anesthesia or sedation within 24 hours prior to MBT
6. No alcohol within 24 hours prior to MBT
7. Patient should be symptom free of any prior intervention (e.g. biopsy)

11.4 Consenting

Patients' and/or their representative will sign a consent form prior to study participation which must be signed and witnessed.

The consent will include willingness to allow acquisition and collation of blood, clinical and imaging data taken on entry to the study and incorporate all other data from time of admission until the patient's termination of the study.

11.5 Safety Termination of Subjects or Study

1. Withdrawal of patients from the study if they have a CTCAE Grade 3 or higher regardless of whether the event is attributed to the drug unless it is caused by an accident that could not reasonably be attributable to the drug (CTCAE: Common Terminology Criteria for Adverse Events Version 4.0).
2. Discontinuance of study, if ≥ 2 patients on Methacetin develop the same CTCAE Grade 3 event or 1 patient develops a CTCAE Grade 4 or higher event due to the breath test.

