11.6 Early Withdrawal from the Study

Patients, their relatives, their representatives or the patients' physician may withdraw the patient from the study at any time if they feel the study is not in the patients' best interest, or they may be withdrawn by the investigator or sponsor for safety, behavioral, or administrative reasons. All withdrawals must be fully documented.

If the patient withdraws from the study and also withdraws consent for the disclosure of future information, no further evaluations should be performed and no additional data should be collected. Previously acquired data will be analyzed. This will not have any effect on the treatment that the patient receives.

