12.7.8.2 Decision Rules

Stop the study in case of severe safety concern.

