16 SAFETY CONSIDERATIONS

16.1 *Adverse Event Definitions*

An adverse event (AE) is any undesirable or unintentional event that occurs in a patient or clinical investigation subject, whether or not considered related to the investigational product; this includes clinically significant changes in laboratory values. As this study is not therapeutic in nature, there will be no therapeutic failures to report.

Regardless of severity or relationship to the study investigational product, all diagnoses, symptom(s), sign(s) or finding(s) with a start date after the first study test has begun (Breath test/EGD) and until the last study procedure is being completed will be documented, assessed by the investigator and recorded in the subject's CRF.

A surgical procedure that was planned prior to the first study test by any physician treating the subject should not be recorded as an AE.

16.2 *Serious Adverse Event (SAE), Unanticipated Adverse Device Effect (UADE) and Suspected Unexpected Serious Adverse Reactions (SUSAR)*

A serious adverse event (SAE) is an event that is either:

- a) Fatal
- b) Life-threatening

Exalenz Bioscience Ltd.	Last update on: Nov 21, 2016
Study Title: Clinical Study of the BreathID[®] MCS System to train the algorithm for the ¹³C-Methacetin Breath Test (MBT) in assessment of Portal Hypertension in Patients with Compensated Liver Cirrhosis	Protocol No.: CSPH-EX-0414 Version: 1.5
Document N^o: CSD00076	Page 48 of 72

Life threatening is defined as an event in which the patient is at risk of death at the time of the event. It does not refer to an event that hypothetically might have caused death if it was more severe.

c) Results in persistent or significant disability/incapacity

Disability is defined as a substantial disruption of a person's ability to conduct normal life functions.

d) Requires or prolongs inpatient hospitalization

e) A congenital anomaly or birth defect.

f) Another serious or important medical event as judged by the investigator.

An Unanticipated Adverse Device Effect (UADE) or a Suspected Unexpected Serious Adverse Reactions (SUSAR) is an SAE, related to the investigational product, for which the nature or severity is not consistent with the expected outcomes of the treatment/testing being offered.

An unexpected adverse event is one that has not been previously observed, or one that is of a specificity or severity not consistent with the current investigator brochure.

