As with every procedure risks and discomforts may occur with relations to the Breath ID test. The potential risks/complications and discomforts which may be associated with all study procedures are listed below.

- Allergic and/or other reactions to BreathID reagent
- Aspiration (inhaling) of food or fluids into the lungs
- Discomfort

When an adverse event occurs, the following information and assessments should be documented in the subject's file and reported in the adverse event section of the CRF:

- The signs, symptoms, or diagnosis of the event if available
- The date and time of onset of the event using the 24 hour clock where midnight is 00:00 and noon is 12:00
- The adverse event severity using the criteria outlined below
- The relationship of the event to the study medical device or drug as outlined below
- Describe any action taken regarding study medical device or drug disposition
- List any required therapy, medication, treatment, or diagnostic procedure.

Exalenz Bioscience Ltd.	Last update on: Nov 21, 2016
Study Title: Clinical Study of the BreathID[®] MCS System to train the algorithm for the ¹³C-Methacetin Breath Test (MBT) in assessment of Portal Hypertension in Patients with Compensated Liver Cirrhosis	Protocol No.: CSPH-EX-0414 Version: 1.5
Document N^o: CSD00076	Page 49 of 72

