16.4 Adverse Event Severity

- **Mild Adverse Events**

A mild adverse event is one that the symptoms are barely noticeable to the patient. It does not influence performance, require drug treatment or prevent the patient from carrying on with normal life activities.

- **Moderate Adverse Events**

A moderate adverse event is one that the symptoms make the patient uncomfortable and causes some impairment to normal life activities. Treatment for symptom(s) may be required.

- **Severe Adverse Events**

A severe adverse event is one that the symptoms cause severe discomforts to the patient and severely limits the patient's normal daily activities. Treatment for symptom(s) is given.

Note: Serious and severe are not synonymous. A serious adverse event must fulfill the requirements listed in the definition above.

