16.5 Adverse Event Reporting

The investigator should report all adverse events in the case report form. The investigator is responsible for the appropriate medical management of all adverse events.

Exalenz Bioscience Ltd.	Last update on: Nov 21, 2016
Study Title: Clinical Study of the BreathID[®] MCS System to train the algorithm for the ¹³C-Methacetin Breath Test (MBT) in assessment of Portal Hypertension in Patients with Compensated Liver Cirrhosis	Protocol No.: CSPH-EX-0414 Version: 1.5
Document N^o: CSD00076	Page 50 of 72

The investigator must report any serious adverse event to the sponsor immediately, within 24 hours of awareness, via email. Full details of the event, severity, outcome (if available) and an assessment of the relationship to the study investigational product must be provided in the report.

All SAEs must be followed up until resolution or stabilization by submission of updated reports. Follow-up SAE reports will be reported according to the same timelines as initial reports, as soon as new significant information becomes available.

All SAEs that fulfill UADE or SUSAR definitions will be reported to the relevant authorities by expedited means.

Notification of the IECs/IRBs and regulatory authorities

Notification to the IECs/IRBs about all relevant events (e.g. SAEs, UADEs, SUSARs) will be performed by the sponsor and/or by the investigator according to all applicable regulations.

The processing and reporting of all relevant events to the regulatory authorities will be done by the sponsor according to all applicable regulations.

If unexpected safety issues are identified, specific amendments will be implemented.

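### The stopping rule runs on CTCAE grades that section 16 does not ask sites to record, and the section 16.6 reporting exemption is not limited to events unrelated to the breath test

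*Combined protocol and SAP*

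**What the plan says.** **Stopping and withdrawal.** Section 11.5 item 2, repeated in the synopsis, discontinues the study if two or more patients given the substrate "develop the same CTCAE Grade 3 event or 1 patient develops a CTCAE Grade 4 or higher event due to the breath test". Item 1 withdraws individual patients "if they have a CTCAE Grade 3 or higher", whatever the attribution, apart from accidents that could not reasonably be put down to the drug. The version is CTCAE 4.0. Section 12.7.8.2 adds a general rule: "Stop the study in case of severe safety concern".

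**Recording.** Section 16.2 lists what goes into the file and CRF for each adverse event, including "The adverse event severity using the criteria outlined below". Those criteria are in 16.4 and have three levels. The top one begins "A severe adverse event is one that the symptoms cause severe discomforts to the patient". Section 16 does not mention CTCAE, and neither does the safety analysis in 12.7.4, which tabulates events by severity and relationship.

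**Reporting.** Section 16.5 states: "The investigator must report any serious adverse event to the sponsor immediately, within 24 hours of awareness, via email". Section 16.6 then exempts listed non-fatal toxicities that meet the SAE definition from expedited notice. They go to the follow-up section of the CRF and are reviewed periodically. The list covers raised bilirubin, raised liver enzymes, nausea, vomiting and diarrhoea, and bleeding after line insertion. It sets no condition on relatedness.

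**Vomiting.** Appendix III says the fluid given for the test may in rare cases cause vomiting, calls this an expected adverse event and directs it to the CRF. Section 10.2, by contrast, expects no adverse events from the breath test.

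**The concern.** A stopping rule works only if the data it needs are collected and reach the person who applies it in time. Here both links are weak.

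First, the rule treats Grade 3 and Grade 4 differently. A single test-related Grade 3 event means continue; a single test-related Grade 4 event means stop. The plan gives no mapping from 16.4 to CTCAE, and both events could be entered as severe.

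Second, the Grade 3 limb needs a count to two across patients. The synopsis lists eight institutions, and only the sponsor sees them all. If one site has a related vomiting SAE at Grade 3 and another site has a second, the rule is met. On the wording of 16.6, neither event has to reach the sponsor promptly. Outside 16.6, the 24-hour duty covers SAEs only, so two non-serious related Grade 3 events could also meet the rule without prompt notice.

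What is at stake is patient safety during enrolment and whether the rule can be audited afterwards. No efficacy result is affected.

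**Working it through.** **Step 1: what the rule needs against what is recorded.**

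| The rule in 11.5 item 2 needs | What section 16 supplies |
|---|---|
| CTCAE grade, with 3 separated from 4 or higher | Mild, moderate or severe (16.4); no mapping |
| Whether the event is due to the breath test | Related or Not Related (16.3): available |
| Same event in two or more patients, across sites | 24-hour notice for SAEs (16.5), minus the 16.6 list; no deadline for non-serious events |

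Relatedness is covered. Grade is not, and timing is covered only in part.

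**Step 2: whether 16.6 is confined to disease events.** It opens with complications of disease progression and says the listed events are anticipated from the disease process. But the list includes bleeding after line insertion, which is procedural, and no item is restricted to unrelated events. The text therefore leaves open whether a test-related vomiting SAE is exempt. The enzyme and bilirubin items matter little here, because the bloods in 13.4.1 are taken before HVPG or drawn from history.

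**Step 3: whether another route catches it.** UADE and SUSAR reporting under 16.2 and 16.5 requires a related SAE whose nature or severity is inconsistent with what is expected. By nature, Appendix III calls vomiting after the drink expected. By severity, a serious case could still qualify. The route is therefore open but depends on judgement.

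**Step 4: how often this could arise.** The plan gives no figure to reproduce, so this is an upper bound from its own safety history in 8.2.1.

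- Inputs: 1,466 chronic liver patients + 74 controls = 1,540 tested with the sponsor's system, with 0 substrate-related events. Published literature: 2,987 individuals with no adverse events reported. Planned N: 200, or up to 400 (12.5).
- One-sided 95% upper limit with 0 events in n: p = 1 − 0.05^(1/n).
- Chance of two or more events: 1 − (1 − p)^N − N·p·(1 − p)^(N − 1).

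| Basis | n | p | N = 200 | N = 400 |
|---|---|---|---|---|
| Sponsor's data | 1,540 | 0.001943 | 0.0584 | 0.1830 |
| Plus published (1,540 + 2,987) | 4,527 | 0.000662 | 0.0080 | 0.0294 |

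The second row assumes that the two sources do not overlap and that the publications reported adverse events fully. Both rows bound related events of *any* grade. Two events that are the same and both Grade 3 are rarer still.

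The length of any delay cannot be estimated, because 16.6 gives no review interval.

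**The case against.** The strongest reply is that the plan already captures most of what matters.

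- **Grading is implied.** Item 1 cannot be applied unless the site judges Grade 3 or higher, and 11.6 adds "All withdrawals must be fully documented". This stands in part. Item 1 uses one class from Grade 3 upwards, so it does not separate 3 from 4, and no deadline for telling the sponsor is attached to a withdrawal.
- **Extremes are identified.** Fatal and life-threatening events are SAE criteria in 16.2: "Life threatening is defined as an event in which the patient is at risk of death at the time of the event". An SAE report also carries full details, from which the sponsor could assign a grade. This stands for SAEs that are reported. It does not reach non-serious Grade 3 events or those that 16.6 exempts.
- **Vomiting during the test has its own record.** Appendix III requires a test termination form, an accountability-log entry and bottles kept for the monitor. This stands as a record, but Appendix III asks for immediate contact with the sponsor only when the device malfunctions.
- **A related vomiting SAE may be a SUSAR or UADE.** The definition includes severity, vomiting is not among the procedure risks listed in 16.2, and 10.2 expects no test-related events. This stands as a real possibility. The Investigator Brochure, which bears on expectedness, is not among the documents.

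A reader might infer that 16.6 deliberately exempts vomiting caused by the test. The documents do not say so: its stated reason is the disease process, and the inference rests only on the missing relatedness condition. The supportable statement is that the wording is ambiguous and, read literally, permits the exemption.

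**Conclusion.** The point holds as a mismatch within the protocol text. The stopping rule depends on CTCAE grades, the specified severity record does not contain them, and the reporting exemption can delay the sponsor's count across sites for a reaction that the protocol itself links to the test drink. It is worth correcting before enrolment but is no reason to hold the study. The safeguards are partial rather than absent, and the any-grade upper bounds (5.8% and 18.3% on the sponsor's data; 0.8% and 2.9% with the literature added) put the actual trigger well into the rare range.

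Two stronger conclusions are not supported. One is that the rule cannot be operated at all: item 1, the SAE criteria, the termination form and the general safety stop would expose many qualifying events. The other is that the Grade 3 limb should be restricted to events caused by the test. In item 2 the attribution to the breath test follows the Grade 4 limb. Whether it also governs the Grade 3 limb is unclear, and narrowing a safety rule would need an argument that the plan does not supply.

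The verdict rests on the protocol text alone. The eCRF is not among the documents; if it already has a CTCAE grade field, the first half of the point is a matter of aligning the text.

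**What to change.** (a) **16.2 and 16.4:** record the CTCAE v4.0 grade of every adverse event in the CRF. Keep mild, moderate and severe for the tables in 12.7.4 if wanted.

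(b) **16.5:** add that every CTCAE Grade 3 or higher event assessed as Related to the device or substrate, serious or not, is notified to the sponsor within 24 hours of awareness. **16.6:** state that its exceptions do not apply to events assessed as Related.

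Leave the scope of 11.5 item 2 as it is. The sponsor should state whether the Grade 3 limb also requires attribution to the breath test. If it does not, the 24-hour notice in (b) would have to cover Grade 3 events of any cause for the count to be timely.

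**Cost:** one CRF field, edits to 16.2, 16.4, 16.5 and 16.6, and a few extra notices. There is no new visit, assessment or change in sample size. Relatedness is already recorded, and the existing severity tables stay as they are.
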